- For patient-reported function we will use the Western Ontario and McMaster Universities Osteoarthritis Index Physical Function Subscale (WOMAC-PF). The score at 3 months will be the primary end point. This instrument was developed based on patient input and is the instrument of choice to assess outcome post-TKR.⁵³ The WOMAC-PF consists of 17 items related to physical function. Each item is scored on a 5-point Likert-type Scale with descriptors from 0-4 (none, mild, moderate, severe, and extreme difficulty). Scores of each item are summed for a maximum total score on the WOMAC-PF of 68. Higher scores indicate worse functional limitations. Reliability and validity of this instrument have been established.⁵⁴⁻⁵⁶ Prior to choosing the WOMAC-PF as the primary outcome, we received input from patients. We asked for 15 patients post TKR to compare the WOMAC, the Lower Extremity Functional Scale (LEFS) and the Knee Outcome Survey (KOS). The patients observed that 4 activities of the LEFS (running on even ground, running on uneven ground, making sharp turns while running fast, and hopping) were not applicable as they are unusual and contra-indicated motions after TKR. They also noted that the focus on symptoms of pain and knee buckling of the KOS were not as relevant to them as the activities limitations queries in the WOMAC. Patients selected the WOMAC as the most patient-centered of the 3 instruments, but added that we should also test their true ability to perform tasks (see below).

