For Aim 2, we plan to assess predictors of response based on a minimum change score of 20% in BOTH the WOMAC-PF and the composite score of functional performance at 3 months, thus yielding a binary outcome. For this aim, we will have a combination of those initially randomized to one of the exercise arms and those in the usual care group who were later randomized to the exercise arms for a total of approximately 200. If the expected response rate ranges between 50% and 60%, we would be able to detect an odds ratio of 2.2 to 2.4 with 80% power assuming a binary predictor with 50% split in the sample. In addition, with approximately 100 responders, we will be able to accommodate 9 predictors in the multiple logistic regression based on rule of thumb guidelines for sample size in logistic regression (min of response/nonresponse/ (#predictors+1) \geq 10).

Data Analysis

[name] will oversee data analyses. We will evaluate the statistical properties of baseline and follow-up outcome measures, including potential outliers, normality and missing data. Measures of central tendency (means, medians, other percentiles) and dispersion (standard deviations, ranges) will be computed for continuous variables, whereas frequency distributions will be calculated for categorical data. Distributions of baseline characteristics will be compared between groups to assess effectiveness of randomization, and statistical or clinical differences will be adjusted in the analyses. Data transformations may be applied if needed and guided by clinical meaningfulness.

Hypothesis 1.1 - Subjects in Groups 1 and 2 will demonstrate better physical function as compared to Group 3.

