The primary outcome of this aim is the WOMAC-PF at 3 months.⁹¹ This analysis will use an intention-to-treat approach. We will analyze this aim using contrasts from a linear mixed models analysis for 3 and 6 month function controlling for baseline function and the randomization covariates (age, gender, BMI, physical function, ROM). We will first explore the intervention by time interaction, and then proceed to a main effects model with only group and time. Our primary interest is the 3 month comparison between the clinic-based individual outpatient exercise and the community-based exercise groups. The linear mixed models allow us to maximize the number of individuals used for the analyses as a person can contribute information at both time points, or just one time point. This analysis is advantageous to conducting a simple baseline adjusted ANCOVA at 3 months because persons missing 3 month data would not be included. The linear mixed model “borrows” information pertaining to the relationship between the 3 and 6 month outcomes such that persons missing either (but not both) can still be used in the analyses. To test if the improvements in outcomes are sustained, we will use contrasts from the linear mixed model at 6 months. For missing 3 and 6 month outcomes see missing data section.

For the battery of performance-based tests we will perform the analyses as described above, one for each measure. For these secondary outcomes we will use Hochberg’s step-up procedure to control the experiment-wise Type I error rate ($\alpha=0.05$),⁹² which otherwise would be inflated due to the multiple endpoints. Hochberg’s procedure is more powerful than Bonferroni adjustment and performs well when the number of endpoints is small and correlated with small to mid-size correlations. For this outcome we will also perform analysis using a composite score formed with unit-weighted z scores of constituent tests to provide a more stable measure of the subjects’ underlying functional performance.⁹³

Hypothesis 1.2- Subjects in Groups 1 and 2 will demonstrate increased physical activity as compared to Group 3.

Adjusted analysis for the outcome of physical activity will parallel the analyses described above for performance-based physical function. The outcomes of this hypothesis are real-time physical activity data captured by the SWM and self-reported physical activity from the CHAMPS questionnaire

PRINCIPAL INVESTIGATOR (LAST, FIRST, MIDDLE): [name]

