Hypothesis 2- A group of baseline biomedical and psychosocial measures will associate with treatment response.

Each subject will be classified as a responder or non-responder based on a minimum change score of 20% in BOTH the WOMAC-PF and the composite score of functional performance at 3 months, thus yielding a binary outcome. Baseline variables will be summarized separately for responders and non-responders. Unadjusted odds ratios will be estimated using univariate logistic regression. To consolidate potential predictors, we will test for collinearity among baseline variables that are associated with response. Baseline measures associated with response at the $p<0.15$ level in unadjusted models will be added to multivariable logistic regression models to assess predictors of treatment response. We will limit the number of predictors going into any one model to no more than one predictor per 10 responses (or 10 non-responses, whichever is less); if more variables are significant, the model will be limited to the most significant variables, after adjusting for those deemed a-priori to be clinically significant. We expect different predictors for each group. For example, patients with worse physical function and impairments (e.g., limited range of motion and muscle weakness) will do better with individual outpatient exercise whereas those with heightened psychosocial factors (e.g., anxiety and depressive symptoms) will respond better to group exercise in the community.^{48,70-72}

Exploratory Hypothesis- Adherence and co-interventions will be similar in all groups. The attrition rate and adverse events- mainly number of falls- will be lower in Groups 1 and 2 compared to Group 3.

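### Aim 2 tests predictors only on a yes/no responder built from two continuous scores, which costs some power for shared effects and much more for predictors of one score alone

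*Combined protocol and SAP*

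**What the plan says.** Data Analysis, Hypothesis 2, defines the outcome: "Each subject will be classified as a responder or non-responder based on a minimum change score of 20% in BOTH the WOMAC-PF and the composite" of the performance tests at 3 months. Baseline variables are then screened one at a time ("Unadjusted odds ratios will be estimated using univariate logistic regression"), and those with p<0.15 enter a multivariable logistic model. No predictor analysis of either score on its own scale is described, even as a sensitivity analysis.

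The Aim 2 paragraph under Sample Size gives the power basis:
- the cohort combines patients first allocated to exercise with usual-care patients "later randomized to the exercise arms for a total of approximately 200";
- "If the expected response rate ranges between 50% and 60" per cent, then "we would be able to detect an odds ratio of 2.2 to 2.4 with 80% power", for a binary predictor split 50/50;
- about 100 responders are said to support nine predictors.

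Both components are continuous. For the WOMAC-PF, "Scores of each item are summed for a maximum total score on the WOMAC-PF of 68" (Outcomes, Physical Function). The performance measure is a "composite score formed with unit-weighted z scores of constituent tests to provide a more stable measure" (Data Analysis, Hypothesis 1.1). That section analyses both on their full scales, but only to compare treatments.

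**The concern.** Cutting a continuous score discards information. A patient who improves by 21% counts the same as one who improves by 80%, while 19% and 21% fall on opposite sides. Requiring both components adds a second loss: if a predictor moves only one score, the other score still decides many patients' status and dilutes the association.

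Aim 2 is meant to show which patients benefit. With about 200 patients, an inefficient outcome raises the chance that a real predictor is missed. The p<0.15 screen uses the same variable, so a predictor can be lost before the multivariable stage. A predictor that is found cannot be traced to self-report, performance or both.

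**Working it through.** **Inputs from the plan.** N about 200, so 100 per predictor level with a 50/50 split; response 50–60%; odds ratio 2.2–2.4; SD 7.7 for WOMAC-PF. Aim 2 states no alpha. Two-sided 0.05 is taken from the primary-endpoint calculation.

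**Assumptions not in the documents.** Outcomes are normal, the two measures have equal thresholds, and their correlation is 0.3, 0.5 or 0.7.

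**1. The plan's own figure.** Two-proportion test with pooled variance:

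power = Φ{[|p2 − p1| − 1.96·√(2p̄(1−p̄)/100)] / √[(p1(1−p1) + p2(1−p2))/100]}

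Solved for 80% power, the odds ratio is 2.26 (50%) and 2.39 (60%) if the response rate is the reference-group rate. It is 2.22 and 2.26 if it is the overall rate. The stated 2.2 to 2.4 is reproduced.

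At odds ratio 2.25 and 50% overall response, the rates are 40% and 60%:
- (0.200 − 1.96 × 0.0707) / 0.0693 = 0.89, so power is 81%.

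**2. Predictor acting equally on both measures.** Let a patient respond when both of two correlated normal scores exceed a threshold c. Choose c so that the lower group responds at 40%, then find the common shift d (in SD) that gives 60%. Power on one continuous score comes from the noncentral t distribution with 198 df and noncentrality d·√(100/2).

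| Correlation | d (SD) | Responder | One score, alpha 0.05 | One score, alpha 0.025 |
|---|---|---|---|---|
| 0.3 | 0.446 | 81% | 88% | 81% |
| 0.5 | 0.464 | 81% | 90% | 85% |
| 0.7 | 0.482 | 81% | 92% | 87% |

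Simulation of Hochberg on the two scores, with the shift set to give exactly 80% power on the responder, gave about 93–96% power to detect the predictor on at least one score (correlation 0.3–0.9). Over correlations from 0 to 0.9, one score at alpha 0.05 has about 83–96%.

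**3. Predictor acting on one measure by 0.5 SD.** On that score the noncentrality is 0.5 × 7.07 = 3.54. Power is 94% at alpha 0.05 and 90% at 0.025. On the responder, at 50% overall response with a favourable shift:

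| Correlation | Responder rates | Odds ratio | Power |
|---|---|---|---|
| 0.3 | 45.3% v 54.7% | 1.46 | 27% |
| 0.5 | 45.6% v 54.4% | 1.42 | 23% |
| 0.7 | 46.1% v 53.9% | 1.37 | 20% |

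The size depends on which component limits response. If the shift is centred (−0.25 v +0.25 SD), responder power is 31–36%. If the predictor worsens the affected score, it is 44–45%. Half or more of the power is lost in each case.

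**4. Detectable effect on the continuous scale.** For 80% power with 100 v 100, d = 0.40 SD at alpha 0.05 (0.398 × 7.7 = 3.1 WOMAC-PF points). At alpha 0.025, d = 0.44 SD (0.439 × 7.7 = 3.4 points).

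**The case against.** **The plan contains no error.** This stands. A reader might infer that the 80% is misstated, or that true power is in the high eighties or nineties. The documents do not support that: 80% is right for the planned test, and the higher figures belong to a different analysis under an assumed correlation. Averaging the two standardised scores would give 96–97% for a shared effect, but averaging is not proposed here, and it would dilute a predictor of one score.

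**Response is deliberately defined as improvement in both domains.** This stands in part. Patients chose the WOMAC and asked for their actual ability to be tested too, so a factor that moves only self-report is, on that definition, not a predictor of response. Whether the responder stays the headline is a choice of clinical target. But the plan also wants to learn which baseline factors relate to functional recovery, and the responder alone cannot separate the components.

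**The documents do not say that any predictor acts on one component.** Correct. It is tempting to assign psychosocial factors to self-report, and strength or range of motion to performance, but the plan states both sets of hypotheses for physical function in general. The single-component case is plausible, not documented.

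**Screening at p<0.15 softens the loss.** At that level, with a single cut on one score, a predictor with odds ratio 2.25 passes with 92% probability, against 98% on the continuous score. A one-measure predictor passes 38–46% of the time. This narrows the gap at the first stage only.

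**The rule is a percentage of each patient's own baseline, not a common threshold.** Also correct, so the figures are indicative.

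**Conclusion.** The concern holds as a loss of efficiency and of interpretability, not as an error in the power statement. For an effect shared by both measures the loss is modest. Relative to 81%, one score gains about 7–11 points unadjusted and about 0–6 points at alpha 0.025; detecting the predictor on at least one score with Hochberg reaches about 93–96%. For a predictor of one measure the loss is large: about 20–27% against about 90% after adjustment, and still no more than 45% under the least unfavourable convention tried. These sizes rest on normality, equal thresholds and a correlation that the documents do not give. They concern a single 50/50 predictor, not the arm-specific predictors that the plan also expects.

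A reader might go further and conclude that the 20% rule is invalid or that the responder analysis should be dropped. Neither follows. The rule's justification is a separate matter, and the responder remains a legitimate clinical summary. The change is a worthwhile, cheap improvement to a secondary aim.

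**What to change.** In the Aim 2 paragraph of Sample Size and under Hypothesis 2:
- Add two linear models, one for 3-month WOMAC-PF and one for the 3-month performance composite. Adjust each for its own baseline, enter the candidate predictors as covariates, and apply Hochberg across the two outcomes (the procedure is already used for the secondary outcomes).
- Preferably use these models for the Aim 2 predictor tests, and keep the odds ratios for response in both components as the clinical summary.
- State the detectable effect for a 50/50 predictor with 200 patients: about 0.40 SD (3.1 WOMAC-PF points at SD 7.7) at alpha 0.05, or 0.44 SD (3.4 points) at the 0.025 step.

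The cost is plan wording and analysis time: screening, collinearity checks and selection are run for two outcomes on data already collected. The two sets of predictor results may differ, and a difference in points is less immediate to patients than a responder. Hochberg across two outcomes does not control error over the many candidate predictors, and the plan should say so.

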Potential Predictors of Treatment Response- Variables at the baseline that we believe may be potential predictors of treatment response, in addition to physical function (described above) include:

- Demographics and Biomedical Characteristics such as age, gender, race, education, BMI, self-rated health (excellent, good, fair, poor, or bad), discharge placement, number of prior rehabilitation sessions, TKR technique, and surgeon experience will be collected.
- Medication prescribed and over-the-counter used for pain will be recorded in the medication form. We will record the current and highest dosage of any pain medication used during the last month.
- Comorbidity data will be gathered using the Cumulative Illness Rating Scale.⁶⁹ Subjects will be asked to indicate conditions with which they have been formally diagnosed by a physician in the past.
- Psychosocial Measures will include factors that our and other groups have demonstrated to be associated with physical function in knee OA and include:^{48,70-72} 1) Fear; 2) Anxiety; 3) Self-Efficacy; 4) Depression; 5) Coping. We hypothesize that patients with higher fear, anxiety, depression and catastrophizing coping along with low self-efficacy who participated in the community-based group exercise classes will be able to improve physical function, whereas the ones who participated in the individual outpatient exercise will not. Fear-avoidance beliefs will be measured by the Tampa Scale for Kinesiophobia.⁷³ Anxiety will be measured using the Beck Anxiety Index.⁷⁴ Self-efficacy will be measured by the Arthritis Self Efficacy Scale.⁷⁵ Depression will be assessed by the Center for Epidemiologic Studies Short Depression Scale.⁷⁶ Coping will be measured by the Coping Strategy Questionnaire.^{77,78}

PRINCIPAL INVESTIGATOR (LAST, FIRST, MIDDLE): [name]

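### Aim 2 counts a 20% change in a z-score composite as response, so responder status depends on an arbitrary zero; a separate, smaller gap is that no arm-by-predictor term is named

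*Combined protocol and SAP*

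**What the plan says.** The Aim 2 paragraph of Sample Size and the Hypothesis 2 paragraph of Data Analysis give the same binary outcome: "a minimum change score of 20% in BOTH the WOMAC-PF and the composite score of functional performance at 3 months". The composite is described once, under Hypothesis 1.1, as a "composite score formed with unit-weighted z scores of constituent tests". No reference mean or SD, direction of scoring, or rule for a zero or negative baseline is given. The six tests (Outcomes, Physical Function) include chair-rise and stair times, where lower is better, alongside measures where higher is better.

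On size, with about 200 patients and a 50-60% response rate, the plan states that "we would be able to detect an odds ratio of 2.2 to 2.4 with 80% power", and that "with approximately 100 responders, we will be able to accommodate 9 predictors in the multiple logistic regression".

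On analysis, "Unadjusted odds ratios will be estimated using univariate logistic regression". Measures reaching p<0.15 go forward: "level in unadjusted models will be added to multivariable logistic regression models to assess predictors of treatment response". Baseline function is a candidate, since the "potential predictors of treatment response, in addition to physical function (described above) include" further lists. The plan also expects predictors to differ by arm. For example, "patients with worse physical function and impairments (e.g., limited range of motion and muscle weakness) will do better with individual outpatient exercise", while patients with heightened psychosocial factors are expected to respond better to group classes. The Psychosocial Measures and Knee Impairments paragraphs make matching arm-specific predictions.

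**The concern.** A percentage of baseline has meaning only on a scale with a true zero. WOMAC-PF (0 to 68) has one; a z score does not. With standardisation to the study baseline, about half the patients start below zero. Dividing by a negative baseline turns an improvement into a negative percentage, and close to zero a trivial change exceeds 20%. Because both limbs are required, a sound WOMAC-PF limb cannot repair the other.

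At stake is whether Aim 2 can be reproduced. The formula and reference would have to be chosen later, possibly with data in hand, for the outcome that is meant to show who benefits.

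The smaller, separable gap is that arm-specific predictions are made but no arm-by-predictor term is named. If one model per arm is intended, significance in one arm and not in the other does not test a difference.

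**Working it through.** **1. The plan's own figures.** Inputs from Sample Size: N = 200, predictor split 50:50, response P = 0.5 to 0.6, power 80%. Two-sided alpha of 0.05 is stated for the primary endpoint and assumed here.

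- Wald formula: ln OR = (1.960 + 0.842) / √(N × P(1−P) × 0.25). For P = 0.5, 2.802/√12.5 = 0.792, OR 2.21. For P = 0.6, 2.802/√12 = 0.809, OR 2.25.
- Two proportions, 100 v 100, with 50% or 60% as the rate in the reference level: OR 2.26 and 2.39.
- Predictors: 100/10 − 1 = 9. At 60% response there are 80 non-responders, and 80/10 − 1 = 7.

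The stated 2.2 to 2.4 and the 9 predictors both reproduce.

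**2. The zero point.** The same gain of 0.3 z units, expressed as a percent change:

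| Baseline composite | Signed baseline | Absolute baseline | Rescaled to 50 + 10z |
|---|---|---|---|
| −1.0 | −30% | +30% | 3/40 = 7.5% |
| 0.05 | +600% | +600% | 3/50.5 = 5.9% |
| 1.0 | +30% | +30% | 3/60 = 5.0% |
| 2.0 | +15% | +15% | 3/70 = 4.3% |

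A reference mean lower by one unit moves a patient from the third row to the fourth, from responder to non-responder, with no change in the data. Rescaling only moves the arbitrary zero.

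**3. Size.** The documents give no inputs for this, so all of the following are assumptions: six aligned tests, inter-test correlation 0.3 or 0.5, per-test reliability 0.9, standardisation to study baseline, mean gain 0.2 or 0.4 composite SD unrelated to baseline, patient SD of gain 0 or 0.3, and the WOMAC-PF limb met independently by 70% or 90%. That makes 16 settings, with 400,000 simulated patients each. Results are for both limbs.

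| Quantity | Signed baseline | Absolute baseline |
|---|---|---|
| Overall response | 21-36% | 38-74% |
| Relabelled when the reference moves 0.5-1 SD | about 15-40% | 5-23% |
| OR, baseline function above v below mean | at least 3.7 | 0.7-0.9 |
| False unadjusted OR, factor unrelated to gain but correlated 0.3-0.5 with baseline function | 1.2-2.45 | 0.85-0.97 |
| That factor passes p<0.15 (samples of 200) | 23-95% | 14-21% |

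Under signed division with the baseline composite in the model, the false OR falls to 0.98-1.10, and p<0.05 occurs in 4-6% of samples.

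**4. The WOMAC-PF limb.** Patient Population requires at least 9 points at entry, so the denominator is safe there. Aim 2 also counts usual-care patients re-randomised after 6 months: about 48 × 0.85 = 41 at the planned 15% attrition. No new baseline or minimum score is stated for them, and Table 1 lists no visit after month 6.

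**5. Arm-by-predictor term.** With four equal cells of 50, SE of the log ratio of ORs = √(4/(50 × P(1−P))). For P = 0.5 this is 0.566, and exp(2.802 × 0.566) = 4.88. For P = 0.6 it is 0.577, giving 5.04. Power for a ratio of 2.2 to 2.4 is 28-34%.

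**The case against.** The strongest reply is that the plan's own procedure contains most of the harm. Every baseline measure with p<0.15 enters the adjusted model, and variables judged clinically important beforehand are adjusted for. Under signed division, the baseline composite passes the screen in 92-100% of simulated samples of 200. If it is offered as a candidate it would nearly always enter, and the false associations would then largely disappear. The 23-95% screen rate is therefore an intermediate step, not a rate of false conclusions. The large false odds ratios also need signed division, a formula that the plan never states. This stands, and it rules out a reading that a reader might infer: that Aim 2 would mainly produce spurious predictors. The documents do not support that.

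Adjustment does not repair the labels themselves, the misleading unadjusted odds ratios under signed division, or the result for baseline function, whose sign depends on the divisor. Under absolute division its odds ratio is no worse than the regression to the mean that an absolute gain also shows (0.67-0.86 at a threshold of 0.3 mean-z).

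Data Analysis allows transformations, and the source cited for the composite may give a reference and a direction. Neither gives a z score a meaningful zero.

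On the second gap, formal Hypothesis 2 claims only association with response, which needs no interaction. The wording on multivariable models leaves arm-specific models possible. Both points stand, so this gap is secondary.

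**Conclusion.** The composite limb is wrong as written. That conclusion follows from the text alone and can be held with high confidence. The magnitudes are illustrative: they rest on the assumptions in step 3 and on normal scores, although single-leg stance is capped at 60 seconds.

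Three further readings are tempting and not supported. The primary analysis of 3-month WOMAC-PF is not touched. The odds ratio of 2.2 to 2.4 is not miscalculated; it is correct for its inputs, but the response rate behind it rests on a rule that does not fix who responds, and it covers pooled predictors only. The 20% WOMAC-PF limb is not defective in general; it is sound at study entry and incomplete only for re-randomised patients.

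The missing arm-by-predictor term leaves the arm-specific expectations without a test. Even with the term, only very large differences between arms could be detected.

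**What to change.** **Responder rule.**
- Keep 20% for WOMAC-PF. State that re-randomised usual-care patients use a score taken at re-randomisation, with a rule for those whose score is then very low or zero.
- Define the composite as the mean of the six test z scores, standardised to the baseline mean and SD of all randomised patients, with chair-rise and stair times reversed.
- Replace the 20% composite limb with a pre-specified absolute gain, in stated units, that the sponsor justifies from measurement error. Sample Size says minimal detectable changes are known for outcomes that include four of the six tests. As a guide, with reliability 0.9 and no true change, the SD of change is √(2 × 0.1/6) = 0.18 mean-z. Thresholds of 0.2, 0.3 and 0.5 mean-z would then label 14%, 5% and 0.3% as composite responders by chance.
- Put the baseline composite in every predictor model, including those used for the p<0.15 screen, and report its coefficient as containing regression to the mean.

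**Arm-specific predictors.** Test each named moderator in its own exploratory logistic model with arm, moderator, arm-by-moderator and baseline composite. About nine moderators are named; entered together they would need 9 + 9 + 1 = 19 terms against an allowance of 9. State that 2.2 to 2.4 applies only to pooled predictors.

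**Cost.** SAP wording, one threshold to justify before analysis, and modest extra analysis; the one possible addition to data collection is a WOMAC-PF score at re-randomisation, if the month 6 score is not used. The 50-60% response rate and the 9-predictor allowance must be rechecked. Under the step 3 assumptions, thresholds of 0.2, 0.3 and 0.5 mean-z give both-limb response of 25-65%, 12-46% and 2-23%. By the plan's own rule a four-term model needs (4 + 1) × 10 = 50 in the smaller class, or 25% of 200, so a strict threshold could rule out even the single-moderator models.

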Calculations of sample size were based on the primary endpoint of WOMAC-PF at 3 months. We propose to recruit a total of 240 subjects (96 in each exercise arm and 48 in the usual care group) to allow approximately 86 subjects in each exercise arm and 43 in the usual care group available for a complete case analysis at 3 months (assuming 10% attrition at 3 months). We propose a larger number of subjects in both exercises groups (outpatient rehabilitative exercise and community-based group exercise) because we expect a moderate effect size between these two interventions; whereas we propose a smaller number of subjects in the usual care group because we expect a large effect size between the usual medical care group and either of the exercise groups. Thus, with an alpha level of 0.05, 2 tails test, a sample size of 172 (n=86 in each exercise group) will provide 81% power to detect a difference as small as 3.3-point difference between the two exercise groups in WOMAC-PF (SD of 7.7 from our pilot work).¹¹ This would correspond to a difference in less than 2 activities (out of the 17 queried in the WOMAC-PF) having improved from “about moderate difficulty” to “no difficulty”. The sample size of 43 in the usual medical care group will provide 80% power to detect a difference of 5.2-point difference in WOMAC-PF between the usual medical care group and any exercise group. Power analysis was conducted in NCSS/PASS. Moreover, this sample size will provide adequate power (above 80%) to test the hypothesis related to the secondary outcomes (performance-based physical function and physical activity). For example, we will be able to detect differences between the two exercise groups as small as 0.7 sec in the stair climbing test, 0.4 in the chair-rise test, 0.02 m/sec in walking speed, 1.4 sec in the single leg stance, and 35 min/day in light intensity physical activity (based on SD of our own preliminary data). The differences we will be able to detect between the usual care and any intervention groups are as small as 1.01 sec in the stair climbing test, 0.54 in the chair-rise test, 0.03 m/sec in walking speed, 1.6 sec in the

PRINCIPAL INVESTIGATOR (LAST, FIRST, MIDDLE): [name]

single leg stance, and 49 min/day in light intensity physical activity. These differences are smaller than the known minimal detectable changes for these outcomes.⁸⁸⁻⁹⁰

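### Aim 2 predictors are screened at p<0.15, then estimated and tested in the same patients with no validation, shrinkage or multiplicity control, so some apparent predictors will be spurious

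*Combined protocol and SAP*

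**What the plan says.** The Hypothesis 2 analysis classes each patient as responder or non-responder at 3 months and fits a separate logistic model for each baseline variable. Variables associated with response at the p<0.15 "level in unadjusted models will be added to multivariable logistic regression models to assess predictors of treatment response". The number entered is limited to "no more than one predictor per 10 responses (or 10 non-responses, whichever is less"; if more variables qualify, "the model will be limited to the most significant variables, after adjusting for those deemed a-priori to be clinically significant". A collinearity check is made among the variables already found to be associated with response. The a-priori variables are not named.

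The Sample Size section pools patients first randomized to exercise with usual-care patients who cross to exercise later, "for a total of approximately 200". It also states that "with approximately 100 responders, we will be able to accommodate 9 predictors in the multiple logistic regression".

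No resampling, split sample, shrinkage, optimism correction or multiplicity control is described for Aim 2. Hochberg's procedure, under Hypothesis 1.1, is specified for the performance tests, and the physical activity analyses are said to follow the same approach.

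**The concern.** A variable that reaches p<0.15 by chance looks stronger in this sample than it is. Refitting it in the same patients and reading its odds ratio, interval and p-value as if it had been chosen beforehand carries that chance excess into the result. The one-per-10 rule does not prevent this, because it counts the variables that survive the screen and not those that were tried.

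Identifying predictors of recovery is one of three study foci in the Design Overview, and Aim 2 is a numbered aim, separate from the plan's Exploratory Hypothesis. At stake is whether the reported predictors, and the strength given to them, would hold up in new patients.

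**Working it through.** **1. The plan's own figures.** The Sample Size section says the study can "detect an odds ratio of 2.2 to 2.4 with 80% power assuming a binary predictor with 50% split in the sample", for response rates of 50% to 60%. The inputs are 200 patients, 100 per predictor level, and two-sided alpha 0.05 (stated for the primary endpoint, assumed here). Power = Φ{[|p1−p0| − 1.96·√(2·p̄·q̄/100)] / √[(p0·q0+p1·q1)/100]}.
- Rate 50% at predictor=0, OR 2.26: p1=0.693, power = Φ(0.84) = 80%.
- Rate 60% at predictor=0, OR 2.39: p1=0.782, power = Φ(0.84) = 80%.

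The stated range is reproduced for one pre-chosen predictor. The model size also follows: 100/(k+1) ≥ 10 gives k=9.

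**2. Number of candidates.** The plan gives no count. Tallying Potential Predictors of Treatment Response, Knee Impairments and Physical Function gives:
- demographic and biomedical 10
- pain medication 1
- comorbidity 1
- psychosocial 5
- impairments 5 (pain in two knees, range of motion, two strength measures)
- function 7 (WOMAC-PF and six performance tests)

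The total is 29. Replacing the six tests by their composite gives 29−6+1 = 24. I take 20 to 35 as an assumed range. Responders per candidate screened are 100/29 = 3.4, not 10.

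**3. Arithmetic if nothing is predictive (29 independent candidates).**
- Expected to pass the screen: 29×0.15 = 4.35.
- At least one passes: 1−0.85^29 = 99.1%.
- At least one of 29 unadjusted tests at p<0.05, with no selection at all: 1−0.95^29 = 77.4%.

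**4. Simulation of the written procedure on pure noise.** Steps: univariable logistic p<0.15, ranking by p, cap at min(responders, non-responders)/10 − 1, then a multivariable refit. There were 1,500 replicates per row, with standard normal candidates and no missing data. The collinearity check and a-priori variables were not modelled.

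| Setting | Mean entered | Cap binds | Mean apparent AUC | Models with a p<0.05 predictor |
|---|---|---|---|---|
| n=200, 29 candidates, 50% response | 4.33 | 2.1% | 0.653 | 74.4% |
| same, correlation 0.5 within domain | 4.25 | 6.2% | 0.638 | 56.1% |
| n=200, 29 candidates, 60% response | 4.15 | 9.4% | 0.655 | 73.6% |
| n=200, 20 candidates, 50% response | 3.00 | 0.1% | 0.625 | 61.5% |
| n=200, 35 candidates, 50% response | 5.13 | 7.7% | 0.668 | 81.9% |
| n=100, 29 candidates, 50% response | 2.78 | 64.2% | 0.688 | 72.2% |
| same, correlation 0.5 within domain | 2.70 | 59.7% | 0.675 | 56.3% |

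Mean AUC in 1,000 new patients was 0.499 to 0.501 in every row. A more heavily clustered correlation structure gave 39% of models with a p<0.05 predictor.

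**5. Odds ratios and intervals** (1,000 noise datasets, n=200, 29 independent candidates). Selected noise variables had a median odds ratio of 1.31 per SD, taken away from 1. Their nominal 95% intervals covered the truth 67% of the time (88% under the heavier clustering). A weak real predictor with true OR 1.25 per SD averaged 1.40 when selected; its coverage was 94%.

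**6. Effect of resampling the selection** (300 noise datasets, 29 independent candidates, n=200). Mean apparent AUC of 0.654 fell to 0.538 with bootstrap correction (60 samples) and to 0.504 with 10-fold cross-validation. Holding all 29 univariable tests to 0.05/29 = 0.0017 gives a family-wise error of 4.9%.

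**The case against.** Several stronger readings are tempting, and the documents do not support them.

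- *The screen causes the false positives.* Most of the roughly three-quarters figure is plain multiplicity: 29 unadjusted tests give 77.4% with no screening. What screening and refitting add is the inflated AUC, the biased odds ratios and the poor coverage.
- *Keeping the strongest variables drives the problem.* That rule applies only above the cap, which binds in about 2% of pooled noise models at 50% response and 9% at 60%. It binds in about 60% to 64% of models at n=100. The plan expects predictors to differ by group but does not say that models will be fitted per arm.
- *Noise will look strongly predictive.* An apparent AUC near 0.65 is modest, and only 11% of pooled noise models (29 independent candidates) reach 0.70. The plan also never mentions AUC; it reports odds ratios.
- *The results will decide which patients get which programme.* The plan expects different predictors by group but states no allocation rule.

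It is also fair that independent candidates are the unfavourable case, since performance tests and psychosocial scales are likely to be correlated. A global null is the worst case too: the plan states directional hypotheses for psychosocial factors and impairments, and some may be true. The collinearity check and a-priori adjustment are real, partial safeguards.

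The core of the concern still stands. The collinearity check follows sight of the outcome, the a-priori variables are unnamed, and neither step corrects optimism. Even the most favourable setting run here (39%) is far above 5%.

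**Conclusion.** The concern holds as a weakness of the stated method for a numbered secondary aim. With 20 to 29 candidates and no true predictor, about 3 to 4 variables would enter, mean apparent AUC would be about 0.62 to 0.65 against 0.50, and about 40% to 75% of final models would show at least one p<0.05 predictor. At 35 independent candidates that last figure reaches 82%. Selected odds ratios are exaggerated, and intervals for noise variables under-cover; for a weak real predictor, coverage was close to nominal.

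These sizes rest on a tallied candidate count, normal predictors, complete data, about 200 patients and a global null. They show what the procedure can produce from noise and do not forecast this trial's result. The primary WOMAC-PF comparison does not depend on them. The change should be made but does not put the main conclusion at risk.

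**What to change.** Name the candidates and the a-priori variables, and keep the latter in every model. Then:

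1. Repeat every step (screen, collinearity check, cap, refit) within at least 500 bootstrap samples or within cross-validation. Report optimism-corrected AUC, calibration slope and each variable's selection frequency. In the noise runs cross-validation came closer to the truth than the bootstrap (0.504 against 0.538), so bootstrap correction should not be presented as complete.
2. Shrink the reported odds ratios by the bootstrap calibration slope, or use penalized logistic regression instead. A corrected AUC alone would leave the odds ratios, intervals and p-values as they are.
3. If p-values are claimed, control multiplicity across all candidates screened. Otherwise label the Aim 2 predictors hypothesis-generating.
4. State whether models are pooled or per arm. If per arm, apply the same steps in each, because that is where the trim to the strongest variables matters.

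The cost is a little more analysis work and more modest reported associations. Penalized coefficients also come without simple p-values. No extra patients or data are needed.
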